6.3 Pharmacokinetic (PK) Analysis Set

The PK Analysis Set will contain all subjects who have received at least 1 dose of investigational product and have at least 1 PK sample collected. These subjects will be evaluated for PK analysis unless the number of data points required for analysis is not enough, or significant protocol deviations have affected the data, or if key dosing or sampling information is missing.

7. Planned Analyses

The following data analyses are planned: (1) dose decision analyses in the dose-escalation cohorts, (2) interim analyses for safety and preliminary efficacy updates, (3) data analysis prior to public disclosures (e.g. scientific meetings), (4) the primary analysis after all dose-escalation and dose-expansion subjects have completed 6 months of treatment, and (5) the final analysis after all subjects have ended the study.

7.1 Interim Analysis and Early Stopping Guidelines

Interim analyses are planned after all subjects in each indication and each phase have ended the study eg, for R/R AML: all subjects enrolled in Group 1 phase 1a, Groups 4 and 5 have ended the study. Interim analyses may be combined if the analysis timing is close or if the number of subjects in each indication or phase is small. Formal interim analyses will be based on locked database.

Ad-hoc interim analyses for safety and preliminary efficacy updates will be performed. Data analysis prior to public disclosures (e.g. scientific meetings) will also be performed.

Safety data will be reviewed on an ongoing basis. Amgen, in consultation with the site investigators, will review in DLRMs all available cumulative data prior to making dose escalation decisions. For R/R AML (Group 1), dose escalation decisions will be made in accordance with a standard 3+3 design using the rules noted below.

- If no DLT is observed within the DLT window in the initial 3 subjects of a cohort, then dose escalation to the next higher dose level cohort will occur.
- If 1 DLT is observed within the DLT window in the initial 3 subjects of a cohort, then the cohort will be expanded to 6 subjects. If no further DLT(s) are observed in the 6 subjects, then dose escalation to the next higher dose level cohort will occur. If ≥ 2 subjects experience a DLT in a cohort, then enrollment into this cohort will be stopped.

Ad-hoc interim analyses and DLRM will be based on as-is snapshot with routine data cleaning. Database will not be locked for these analyses.

Dose escalation will occur at the planned dose levels until the MTD is determined or until the highest dose level is tested. The MTD is defined as the highest dose level with an observed incidence of DLT in < 33% of subjects enrolled in a cohort dose level. At least 6 evaluable subjects will be treated at the MTD or highest tested dose.

The mTPI-2 model will be used to make dosing recommendations for Group 2 and Group 3 (see [section 3.3](#) for details). Adverse events and DLTs observed in all subjects will be

evaluated continually and fully integrated into all DLRMs and considered in all enrollment and dosing decisions.

Enrollment of a cohort can be suspended at any time based on safety findings at any dose level and in the expansion cohort, if at any time $\geq 33\%$ of subjects treated at the MTD (including those treated at the MTD in the expansion phase) or RP2D experience a DLT within the DLT window, and a DLRM will be convened. In addition, the study may be discontinued or modified at any time due to documented safety findings.

Dose Level Review Team (DLRT)

For each group, DLRMs will be held to review data, monitor safety, and make recommendations on dose escalation / change, or changes in pre-medication. The DLRT will be composed of the investigators or designees, and the following Amgen representatives: early development leader, medical monitor, global safety officer or designee, clinical study manager, biostatistician, PK scientist (optional), and other functional area representatives as appropriate. A quorum as defined below must be in attendance for the DLRM. The quorum is defined as $> 50\%$ of the participating investigators or their qualified designee (ie, sub-investigator or research nurse or study coordinator possessing written documentation [eg e-mail] of the investigator's vote), as well as $> 50\%$ of Amgen representatives listed above. The early development leader or designee must attend for the quorum to be reached. The DLRM will be rescheduled if a quorum is not reached.

The required voting members of the DLRT include: investigators, Amgen medical monitor, early development leader, and global safety officer or designee.

The following recommendations can be made by the DLRT:

- dose escalation / de-escalation decisions
- expansion of a cohort
- continuation, delay or termination of dosing
- implementation of dose step(s)
- extension of the run-in phase in case of dose step(s)
- extension of the duration of treatment cycles
- implementation of mandatory steroid pre-treatment in case of cytokine release syndrome-related adverse events
- enrollment of additional subjects in the expansion cohort
- duration of the DLT period based on emergent safety data

- level and duration of dose steps (schedule) adjustment based on safety, and available PK and PD data

All available study data, including demographics, IP administration, medical history, concomitant medications, adverse events, ECGs, vital signs, laboratory data, and PK/PD information will be reviewed. In addition to DLTs, all \geq grade 3 toxicities not meeting DLT criteria will be reviewed and may be considered in DLRT recommendations. Data will not need to be source data verified and queries will not need to be resolved prior to the DLRM.

Subject's cytogenetic profiles (eg, potentially higher cytokine release in monocytic AML) should be taken into consideration for DLRT recommendations.

In the expansion phase, all available study data will be reviewed (with recruitment ongoing) by the DLRT once the first 5 subjects have at least completed their first treatment cycle plus two weeks or dropped out of treatment / study, whichever occurs earlier. Once the first 10 subjects have at least completed their first treatment cycle plus two weeks or dropped out of study, all available study data will be reviewed by the DLRT. If there is at least 1 responding subject within these first 10 subjects, the DLRT will determine if an additional (up to 20) subjects may be enrolled. If additional subjects are enrolled after the first 10 subjects, all available study data will be reviewed (with recruitment ongoing) by the DLRT after every 5 subjects have at least completed their first treatment cycle plus two weeks or dropped out of treatment / study. Ad hoc meetings may be convened any time in case of important safety events

7.2 Primary Analysis

The primary analysis will occur when target enrollment is complete and each subject either completes 6 months on study or terminated the study early. Primary analysis will be based on locked database to prevent further changes.

7.3 Final Analysis

A final analysis is planned after all dose-escalation cohorts and dose-expansion subjects have ended the study. Primary and final analysis may be combined in case all subjects have ended study approximately 6 months after enrollment of the last study subject. Final analysis will be based on locked database to prevent further changes.

8. Data Screening and Acceptance

8.1 General Principles

The objective of the data screening is to assess the quantity, quality, and statistical characteristics of the data relative to the requirements of the planned analyses.

8.2 Data Handling and Electronic Transfer of Data

Amgen's Clinical Data Management department will provide all data to be used in the planned analyses. Details of PK, Antibody, and external lab data transfer to the database will be outlined in the Clinical Data Management Plan (DMP). See details of this section in the DMP. This study will use the RAVE database.

8.3 Handling of Missing and Incomplete Data

The following imputation for missing or incomplete data will be performed if required: Incomplete adverse event and concomitant medication dates missing data will be imputed as described in [Appendix A](#).

Non-pharmacokinetic measurements (eg, biomarker data) that are below the lower limit of quantification will be considered equal to half of the lower limit of quantification for all analyses unless specified otherwise.

- Laboratory measurements that are below the quantification limits will be considered equal to the lower limit of quantification for all analyses unless explicitly noted otherwise.
- Biomarker data that are below the quantification limits will be considered equal to half of the lower limit of quantification for all analyses unless specified otherwise.
- PD concentrations that are below the quantification limits will be set to zero when engaging non-compartmental model to compute PD parameters.

8.4 Detection of Bias

Lack of protocol compliance and the potential for biased statistical analyses will be examined by assessing the incidence of important protocol deviations in each cohort. The clinical study team will identify and document the criteria for important protocol deviations.

8.5 Outliers

PK concentration data will be evaluated for outliers by visual inspection and decisions to re-assay individual samples will be made in accordance with standard CPMS practices. All excluded observations will be detailed by CPMS along with reasons for exclusion, in accordance with standard CPMS practices.

Pharmacodynamic (PD) concentration data will be evaluated for outliers by visual inspection, and decisions to re-assay individual samples will be made in accordance with standard PD evaluation practice. Descriptive statistics will be used to identify potential outliers in key variables.

Suspected outliers will be included in all analyses unless there is sufficient scientific justification to exclude them.

8.6 Distributional Characteristics

Where appropriate, the assumptions underlying the proposed statistical methodologies will be assessed. If required, data transformations or alternative non-parametric methods of analyses will be utilized.

8.7 Validation of Statistical Analyses

Programs will be developed and maintained and output will be verified in accordance with current risk-based quality control procedures.

Tables, figures and listings will be produced with validated standard macro programs where standard macros can produce the specified outputs.

The production environment for statistical analyses consists of Amgen-supported versions of statistical analysis software, for example the SAS System version 9.4 or later.

9. Statistical Methods of Analysis

9.1 General Considerations

Descriptive statistics will be provided for selected demographic, safety, PK, PD and biomarker data by dose, dose schedule, time as appropriate, and each indication (Group1, Group2, Group3) separately. Unless otherwise stated, the data analysis will be conducted using subjects in the Safety Analysis Set. Descriptive statistics on continuous data will include means, medians, standard deviations, and ranges, while categorical data will be summarized using frequency counts and percentages. Graphical summaries of the data may also be presented. When data are summarized by time, the values recorded against the scheduled time points listed in the protocol will be used. When assessing minimum/maximum increases or decreases over the study, all assessments, including unscheduled assessments will be used. Data listings will include all available data from all enrolled subjects unless specified otherwise. Additional analysis for Group 4 and Group 5 will be specified in SSAP.

Data analysis will occur at the following time points:

- Interim analyses as described in [Section 7.1](#).
- The primary analysis will occur when target enrollment is complete and each subject either completes 6 months on study or terminated the study early.

- A final analysis is planned after all dose-escalation cohorts and dose-expansion subjects have ended the study.

Confidence intervals 80% and 95% (CI) for proportions will be estimated using an exact method proposed by [Clopper and Pearson, 1934](#).

9.2 Subject Accountability

A summary of subject disposition with discontinuation reasons, and AMG 330 completion and discontinuation will be provided. Key study dates for the first subject enrolled, last subject enrolled, and last subject's end of study will be presented.

9.3 Important Protocol Deviations

Important Protocol Deviations (IPDs) categories are defined by the study team before the first subject's initial visit and updated during the IPD reviews throughout the study prior to database lock. These definitions of IPD categories, subcategory codes, and descriptions will be used during course of the study. Eligibility deviations are defined in the protocol. A subject listing and summary table will be provided for Important Protocol Deviations.

9.4 Demographic and Baseline Characteristics

The following demographic and baseline characteristic will be summarized using descriptive statistics. If multiple races have been reported for a subject, the subject will be categorized as multiple race as well as by the combination of race.

The baseline characteristics to be summarized include:

Demographic

- Sex: Male, Female
- Age: 18-64, 65-74, 75-84, >=85
- Race: American Indian or Alaska Native, Asian, Black or African American, Native Hawaiian or Other Pacific Islander, White, Other
- Ethnicity: Hispanic or Latino, Not Hispanic or Latino

Baseline characteristics for R/R AML

- Height
- Weight
- Eastern Cooperative Oncology Group (ECOG) Performance Status
- Type of AML (at initial diagnosis and at study entry)
- Prior lines of therapies

- Responses to the prior lines of therapies
- Prior hematopoietic stem cell transplant
- Disease duration
- Bone marrow blast
- Baseline Tumor Burden
- ELN risk classification (at initial diagnosis and at study entry)
- White blood cells
- Absolute Neutrophil count
- Platelet count

Baseline characteristics for MRD

- Height
- Weight
- Eastern Cooperative Oncology Group (ECOG) Performance Status
- Type of AML (at initial diagnosis and at study entry)
- MRD status
- Prior lines of therapies
- Responses to the prior lines of therapies
- Prior hematopoietic stem cell transplant
- Disease duration
- Bone marrow blast
- Baseline Tumor Burden
- White blood cells
- Absolute Neutrophil count
- Platelet count

Baseline characteristics for MDS

- Height
- Weight
- Eastern Cooperative Oncology Group (ECOG) Performance Status
- Type of MDS (at initial diagnosis and at study entry)
- MDS Risk(IPSS-R) (at initial diagnosis and at study entry)

- MDS status at study entry
- Prior lines of therapies
- Responses to the prior lines of therapies
- Prior hematopoietic stem cell transplant
- Disease duration
- Bone marrow blast
- Baseline Tumor Burden
- White blood cells
- Absolute Neutrophil count
- Platelet count

9.5 Efficacy Analyses

9.5.1 Analyses of Primary Efficacy Endpoint(s)

No efficacy parameter is considered in primary endpoints

9.5.2 Analyses of Secondary Efficacy Endpoint(s)

The proportion of subjects with an overall response ([Section 5.4](#)) with corresponding exact 80% and 95% Confidence Intervals will be calculated using the Clopper-Pearson method ([Clopper and Pearson, 1934](#)) by cohort. The proportion of subjects who are event-free at 6 months with corresponding exact 80% CI will be calculated using the Clopper-Pearson method. The proportion of subjects with MRD response at the 0.1% threshold and the 0.01% threshold amongst subjects in the Safety Analysis Set will be summarized by cohort.

Listings indicating time to response, duration of response (DOR), and event-free survival will be produced for responders for each indication separately. For subjects in dose expansion cohorts, Kaplan Meier curves may be presented for event-free survival and overall survival with estimates for rates and 80% CI at selected weeks. DOR and time to response will only be analyzed for subjects who achieved an overall response.

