#### **3.5.1 Study Duration for Subjects**

It is anticipated that an individual subject will participate in the study for up to 6 months including a screening period lasting 14 days, a treatment period lasting approximately 4 months, and a safety follow-up period lasting approximately 4 weeks. The actual duration for individual subjects will vary depending upon tolerability of AMG 330, evidence of clinical progression, and willingness to participate in the study.

After completion of a first cycle without a DLT, up to 5 additional treatment cycles can be administered as long as in the judgment of the investigator the subject is deriving benefit.

End of study (EOS) for an individual subject is defined as the date of the final study visit (EOS visit) when assessments and procedures are performed. The EOS visit should occur approximately 4 weeks (+ 1 week) after the last dose of AMG 330 or prior to the initiation of other AML therapy, whichever occurs earlier. Subjects who complete the EOS visit will be considered to have completed the study.

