## **8.3           Reasons for Removal From Treatment or Study**

### **8.3.1       Reasons for Removal From Treatment**

Reasons for removal from protocol-required investigational product(s) include any of the following:

- Subject request
- Safety concern (eg, due to an adverse event, non-compliance, requirement for alternative therapy, or pregnancy)
- Death
- Lost to follow-up
- Confirmed disease progression as defined by revised IWG response criteria and ELN response criteria ([Appendix E](#), [Appendix K](#) and [Appendix M](#)) or disease progression accompanied by worsening of symptoms or deterioration of the subject's general condition
- Protocol specified criteria:

- Proceeding to HSCT

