- Efficacy parameters for R/R AML: response rate (response defined as CR/CRi/morphologic leukemia-free state [per modified IWG criteria] or CRh), duration of response, time to response, event-free survival and overall survival (duration of response, event-free survival, and overall survival will only be measured in the expansion cohort)
- Efficacy parameters for MRD-positive AML: response rate (response defined as conversion from MRD+ status with 0.1% threshold to MRD-), time to response,

relapse-free survival, and overall survival (relapse-free survival and overall survival will only be measured in the expansion cohort)

- Efficacy parameters for MDS: response rate (response defined as CR or marrow complete remission [per International Working Group (IWG) standardized response criteria]), duration of response, time to response, event-free survival and overall survival (duration of response, event-free survival, and overall survival will only be measured in the expansion cohort)

Exploratory Endpoints:

- Depletion of LSCs
- MRD response
- Lymphocyte counts, cluster of differentiation (CD) 33+ monocytes and T cells, as well as T cell activation (including T cell subsets). Other immune subsets may also be examined
- [REDACTED]
- [REDACTED]
- [REDACTED]
- Changes in serum cytokine levels
- Frequency and severity of cytokine release syndrome (CRS) and other AEs following [REDACTED] premedication, and alternative dose step schedules of AMG330
- [REDACTED]

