5.3 Study Dates

Informed Consent Date

The date on which the subject signs the informed consent form.

Enrollment Date

Enrollment date is defined as the date collected on the Subject Enrollment CRF page.

Study Day 1

Study Day 1 is defined as the first day that AMG 330 is administered to the subject.

Study Day

If date is on or after first administration of AMG 330: study day= (date - date of Study Day 1) + 1

If date is prior to date of first administration of AMG 330: study day= (date – date of Study Day 1)

Last Investigational Product Dose Date

The last IP dose date for each subject is defined as the end date of last infusion of AMG330.

End of Investigational Product (IP) Administration Date

End of IP Administration for each subject is defined as the date of decision was made to end IP reported on the End of IP Administration CRF page.

End of study (EOS)

End of study for an individual subject is defined as the date of the final study visit (EOS visit) when assessments and procedures are performed. The EOS visit should occur approximately 4 weeks (+ 1 week) after the last dose of AMG 330 or prior to the initiation of other AML therapy, whichever occurs earlier. Subjects who complete the EOS visit will be considered to have completed the study.

Death Date

For subjects who die during the study, the death date will be recorded on the end of study CRF in the “date subject ended study” field. Incomplete death dates where only the day of death date is missing will be imputed using the following rules:

Day 1 of the month will be used if year and month indicate that death happened in different month from last known alive date;

One day after last known alive date will be used if death happened in the same month as last known alive date.

The imputed death date will be used in calculation of duration of response, progression-free survival and overall survival.

Last Known Alive Date

For subjects not known to have died, their last date known to be alive will be determined as the latest date associated with clinic visits before data cutoff date including, for example, but not limited to the following:

- Date of Enrollment on Subject Enrollment CRF
- Date First Taken, Date Last Taken on Concomitant Medications CRF
- Date Performed on ECOG Performance Status, Vital Signs, Electrocardiogram, Procedures CRFs
- Admission Date, Discharge Date on Hospitalizations CRF
- Date of Examination on Physical Measurement CRF

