Duration of response is defined as the interval from the date of the first disease assessment indicating an overall response to the first documented relapse, disease progression, or death due to any cause, whichever occurs first. Subjects without relapse, disease progression or death until the analysis data cut-off date will be censored at the last adequate disease assessment date. Only subjects with a response will be evaluated for DOR.

DOR time in days = earlier of (date of first relapse or disease progression or death or date of censoring) – date of the first observation of overall response +1.

DOR time in months= earlier of (date of first relapse or disease progression or death or date of censoring) – (date of the first observation of overall response +1)/30.4

Overall Survival (OS)

Overall survival is defined as the time from enrollment until death due to any cause.

Subjects alive will be censored at the last known date. If the date last known to be alive is after the date that triggers the analysis (ie, the data cutoff date), the subject will be censored at the date of last contact through the analysis trigger date.

Event-free Survival:

Event-free survival (EFS) is defined as the interval from first administration of AMG 330 to the earliest of date of treatment failure, relapse for responders, or death due to any cause. Censoring is at the last evaluable post-baseline response assessment; otherwise,

at first administration of AMG330. For non-responders, the event date for treatment failure is assigned as the date of first administration of AMG 330.

Event-free Survival in days = earlier of (date of treatment failure or relapse or death or date of censoring) – date of the first administration of AMG 330 +1.

Event-free Survival in months = earlier of (date of treatment failure or relapse or death or date of censoring) – (date of the first administration of AMG 330 +1)/30.4.

Time to Response (TTR)

Time to response defined as the interval from the first administration of AMG 330 to the first documentation of response. Time to response is evaluated only for subjects who achieved a response.

Time to response is calculated as the number of days:

(date of first response – date of study day 1 +1).

6. Analysis Sets

The analysis of all endpoints, unless noted otherwise, will be conducted on the Safety analysis set defined in [Section 6.1](#).

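### The SAP's month formulas for EFS and DOR divide only the start date by 30.4, and its 6-month event-free proportion has no rule for responders censored before month 6

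*SAP*

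**What the plan says.** **The 6-month rate.** SAP 9.5.2 plans a simple proportion: "The proportion of subjects who are event-free at 6 months with corresponding exact 80% CI will be calculated using the Clopper-Pearson method". The same section makes the time-to-event version optional and confines it to expansion cohorts: "Kaplan Meier curves may be presented for event-free survival and overall survival with estimates for rates and 80% CI at selected weeks".

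**Where EFS is measured.** SAP 2.1, for R/R AML and for MDS: "duration of response, event-free survival, and overall survival will only be measured in the expansion cohort". MRD+ AML has relapse-free survival instead.

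**How EFS is censored.** SAP 5.4: "Censoring is at the last evaluable post-baseline response assessment", or at first dose if there is no such assessment. Non-responders have their event on the day of first dose.

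**Month formulas.** In SAP 5.4 the day versions of EFS and DOR are correct: end date minus start date plus 1. In the month versions the bracket closes around the start date plus 1, so only that term is divided by 30.4.

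**Follow-up.** Protocol 3.5.1 anticipates "a treatment period lasting approximately 4 months, and a safety follow-up period lasting approximately 4 weeks". SAP 5.3 puts the end-of-study (EOS) visit about 4 weeks (+1 week) "after the last dose of AMG 330 or prior to the initiation of other AML therapy, whichever occurs earlier". Protocol 8.3.1 lists "Proceeding to HSCT" among the reasons for removal from treatment. Against this, SAP Section 7 times the primary analysis for when "subjects have completed 6 months of treatment", while SAP 7.2 also admits subjects who ended the study early.

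**The concern.** A Clopper-Pearson interval takes a count of successes out of a fixed number of subjects. A responder last assessed as event-free on, say, day 140 is neither a success nor a failure at month 6 until a rule makes the subject one. The Safety Analysis Set (SAP 6.1) fixes the denominator. SAP 8.3 and Appendix A deal with adverse event, medication and death dates and with quantification limits. None of these supplies the numerator.

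Because non-responders fail on day 1, the numerator is a handful of responders, so each unresolved case shows. Two programmers working from the same data could report different 6-month rates.

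The month formulas are a separate defect: a stated derivation that returns a wrong value if programmed as printed.

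**Working it through.** **1. The plan's own intervals.** SAP 3.2 gives exact 80% intervals for a 20% response rate. Clopper-Pearson with 10% in each tail gives 5.5% to 45.0% for 2/10 and 10.9% to 32.5% for 6/30. Both agree with the plan, so the same function is used below.

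**2. Month formulas.** Take a first dose on day number 22500 and an event on 22681, with dates stored as days from a fixed origin.
- As printed: 22681 − (22500 + 1)/30.4 = 22681 − 740.2 = 21,940.8.
- Bracket moved: (22681 − 22500 + 1)/30.4 = 182/30.4 = 5.99 months.

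The DOR formula has the same form and the same fault. SAP Appendix C prints the DOR month formula with the bracket in the right place, which supports the intended reading.

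**3. Shift per early-censored responder.** Counting one subject as event-free or not changes the proportion by 1/n: 1/30 = 3.3 points, 1/10 = 10 points. This needs no assumption about how censoring arises.

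**4. Illustration.** Assumed: n = 30 and 6 responders (the plan's 20%). Two relapse, on days 90 and 165; two are censored, on days 140 and 150; two are event-free past month 6. The days are invented to show the mechanism.

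| Rule | 6-month rate | 80% CI |
|---|---|---|
| Censored counted as not event-free | 2/30 = 6.7% | 1.8–16.8% |
| Censored counted as event-free | 4/30 = 13.3% | 5.9–24.9% |
| Kaplan-Meier: 6/30 × 5/6 × 2/3 | 11.1% | 4.6–20.8% (log-log), 2 at risk |

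The first two rows bound the observed proportion whatever caused the censoring. Kaplan-Meier is 11.1 − 6.7 = 4.4 points too high if both censored subjects would have relapsed before month 6, and 13.3 − 11.1 = 2.2 points too low if both would have stayed event-free.

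**5. Could censoring fall before month 6?** With the SAP's 30.4-day month, month 6 is 6 × 30.4 = 182.4 days.
- Anticipated course in Protocol 3.5.1: 4 × 30.4 + 28 to 35 = 150 to 157 days. This is before month 6.
- Six 28-day cycles without gaps: 6 × 28 + 28 = day 196; with 1-week gaps: 6 × 28 + 5 × 7 + 28 = day 231. Both are after month 6.
- Six 14-day cycles with 1-week gaps: 6 × 14 + 5 × 7 + 28 = day 147; with 2-week gaps: 6 × 14 + 5 × 14 + 28 = day 182. The 14-day schedule tables apply to Group 1 only, so this case does not arise in MDS.

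These are EOS days, whereas EFS is censored at the last evaluable response assessment. For a gap-free subject on six 28-day cycles, the cycle 6 day 29 marrow falls on day 5 × 28 + 29 = 169. If the EOS marrow were missing or not evaluable, that subject too would be censored before month 6.

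**The case against.** The strongest reply is that a plain reading already exists. The denominator defaults to the Safety Analysis Set, and a subject last assessed on day 140 has not been shown to be event-free at month 6, so taken literally the sentence gives the conservative count. That is a reasonable reading, and it is the one the fix adopts. It is not written down, however, and SAP 5.4's censoring rule invites a programmer to read the subject differently.

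Second, a reader might infer that most responders will be censored before month 6. The documents do not support that. Protocol 3.5.1 describes an anticipated course, says that actual duration will vary, and allows up to five further cycles while the subject benefits; responders are the likeliest to use them. SAP Section 10 adds EFS in anticipation of Amendment 10 and mentions long-term follow-up, and SAP 5.3 lists a survival status form, so longer follow-up may be coming. Survival follow-up does not guarantee response assessments, and longer follow-up would reduce the number of such cases without saying how to count the rest. The frequency is unknown.

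Third, a reader might infer that the binomial is the wrong method and that Kaplan-Meier should replace it. That also goes too far. A binomial with a stated conservative count is legitimate. Censoring when other therapy or transplant begins may be informative, which weakens Kaplan-Meier, and few subjects may be at risk at month 6.

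Fourth, the bracket error is editorial, and a result of thousands of months would be noticed. That is true of its practical effect; the formula still needs correcting.

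**Conclusion.** Two defects hold, both minor.

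1. The EFS and DOR month formulas in SAP 5.4 are wrong as written. This rests on the printed text alone. The practical effect is small, because the adjacent day formulas are right and the error would be obvious in output.

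2. The 6-month event-free proportion in SAP 9.5.2 lacks a counting rule for responders censored before month 6, in the R/R AML and MDS expansion cohorts. The only size that needs no assumption is 3.3 points per such responder at n = 30 and 10 points at n = 10. The 6.7%, 13.3% and 11.1% figures depend on assumed event and censoring days and are not predictions.

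The stakes are low. Protocol 10.4.3.2 calls the efficacy analyses exploratory, SAP 9.5.1 has no primary efficacy endpoint, no decision rule uses this rate, and EFS is also listed for each responder.

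**What to change.** - **SAP 5.4:** write both month formulas as (earlier of event or censoring date − start date + 1)/30.4. The start date is the first dose for EFS and the first observed response for DOR.
- **SAP 9.5.2, counting rule:** keep the Clopper-Pearson proportion on the Safety Analysis Set for the expansion cohorts where EFS is measured. State that subjects censored before month 6 count as not shown to be event-free, and report how many there were. This also covers a subject censored at first dose for lack of any post-baseline assessment. Give month 6 in days (182 if the 30.4-day month is meant).
- **SAP 9.5.2, Kaplan-Meier:** change *may* to *will* for the 6-month EFS rate, with its 80% CI and the number at risk, shown beside the binomial. Omit it if nobody is at risk at month 6. Neither estimate replaces the other.

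The cost is SAP wording and one output that is already optional. The downside is a wide interval in a small cohort, and in some cohorts a Kaplan-Meier rate that cannot be reported at month 6.
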